## **6.9 Missing Data Handling**

The missing data pertinent to the validated instrument ASIS will be handled per instrument owner instructions / scoring manual. For effectiveness measures obtained from Site Investigators and Subjects, namely, IGA, PtGA (from ASIS item # 9) and Patient appearance rating scale (from ASIS item # 10), LOCF data imputation method will be used to impute

responses for Week 12 for the Subjects with missing data at Week 12. LOCF will also be used to impute responses for Weeks 4 & 8 for the Subjects with missing data at those encounters for these select measures, as appropriate. For all other study variables and endpoints, no missing data imputation is planned.

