### **3.1 Subject Inclusion Criteria**

**Patient Inclusion Criteria:** In order to be eligible to participate in this study, an individual must meet all of the following criteria:

- Male or female, aged 9 years and above at the time of study recruitment.
- Has facial non-nodular AV with IGA score of moderate (3) or severe (4).
- Considered as a potential candidate for sarecycline treatment to manage their AV, per clinician's judgment.
- Able to read and write English.
- Provide consent (in case of adult patients) or assent (in case of pediatric patients) to participate in the study.
- Willing to comply with all study procedures and be available for the duration of the study.

**Caregiver Inclusion Criteria:** In order to be eligible to participate in this study, an individual must meet all of the following criteria:

- Male or female, aged 18 years and above.
- Able to read and write English.
- Primary caregiver of the study-eligible patient.
- Provide consent to participate in the study.
- Willing to comply with all study procedures and be available for the duration of the study.

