#### **6.6.4 CFB in PROs**

CFB in ASIS domain scores and subscale scores at Week 12 will be assessed (estimated as Week 12 score minus Baseline score). CFB will be first analyzed descriptively for the entire FAS cohort. For this analysis of domain scores, measures will be considered as continuous variables. No missing data imputation will be used. CFB in proportion of individuals reporting specific response for individual items of ASIS will be conducted by treating these variables as discrete variables, and grouping into top-2 or bottom-2 response scales (within the likert scale), as outlined in Section 6.3.1. Scoring, scaling, and the handling of missing data will be handled in accordance with the recommendations accompanying the ASIS documentation.

CFB in proportion of individuals reporting specific response for select individual items of ASIS, most specifically, items # 9 & 10, will be conducted by treating these variables as discrete variables, and grouping into top-2 or bottom-2 response scales (within the likert scale), as outlined in Section 6.3.1. CFB at Weeks 4 & 8 will be assessed in addition to Week 12. LOCF data imputation method will be used to impute responses to ASIS items # 9 & 10 for respective encounters for the Subjects with missing data at those encounters, prior to analyses. CFB for these two measures (with and without LOCF imputation) will be first analyzed descriptively for the entire cohort, and then analyzed for select subgroups (as outlined in Section 6.3.2) with measures that use LOCF imputation.

Items from EPQ will be analyzed individually and CFB in individual questions/items will be reported descriptively for relevant categories of responses (depending on the response scales). No missing data imputation will be undertaken for these items.

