#### **6.6.5 Comparison of Parent/Caregiver and Patient Perceptions of AV Severity and Impact**

Parent/caregiver and pediatric patient responses to the questions related to AV severity at Baseline and Week 12 will be compared and reported using descriptive statistics, to portray the

level of concordance/discordance in stakeholder perceptions, within the Subject age group of 12-17 yrs. This analysis will be conducted using FAS.

Responses to select EPQ items at Baseline and Week 12 related to worries about Acne and impact of acne on child's ability to reach future goals will be compared to corresponding questions to parents/caregivers to portray the level of concordance/discordance in stakeholder perceptions, within the Subject age group of 12-17 yrs. This analysis will be conducted using FAS.

Parent/caregiver and pediatric patient responses to the questions at Week 12 related to the parents' understanding of child's concerns will be compared and reported using descriptive statistics, to portray the level of concordance/discordance in stakeholder perceptions, within the Subject age group of 12-17 yrs. This analysis will be conducted for the entire relevant cohort using FAS.

No missing data imputation will be undertaken for these items.

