## 6.10 Significant Protocol Deviations

A protocol deviation is defined as any intentional or unintentional failure to follow the requirements and procedures described in the study protocol. Deviations may have occurred at the subject level or at the site level, and could have been recorded by the site, or uncovered data review. Considering the real-world study design of PROSES, reflecting the routine clinical practices in the U.S and associated patient encounters and routine/standard of care data documentation, patients are expected to miss clinic visits or reschedule planned visits as life situations change. These will not be considered as protocol deviations.

Significant protocol deviations will be flagged, and these are defined as study-related issues that were likely to result in: significant impairment of the rights, welfare or safety of subjects; misconduct and/or fraud; and significant impairment of the integrity/validity of study results. Significant protocol deviations also include issues that were likely to impair monitoring and oversight of the study.

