## 7.2 Tables from clinician's DCF (FAS Population)

Clinician data is analyzed using the FAS dataset. In relevant instances (such as IGA and physician satisfaction evaluations), only FAS dataset with corresponding week 12 clinician data is used. All data tables in this section correspond to FAS population.

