**Table 7.2.4.5 Sub-group Analysis of IGA (with LOCF imputation)**

	% Clear/Almost Clear			
	Weeks			
	Baseline (N=x)	Week 4 (N=x)	Week 8 (N=x)	Week 12 (N=x)
Sex				
Male	n (%)	n (%)	n (%)	n (%)
Female	n (%)	n (%)	n (%)	n (%)
p-value	p	p	p	p
Age Group				
≥ 9 and < 12 years	n (%)	n (%)	n (%)	n (%)
≥ 12 and < 18 years	n (%)	n (%)	n (%)	n (%)
≥ 12 years	n (%)	n (%)	n (%)	n (%)
p-value	p	p	p	p
Race				
White	n (%)	n (%)	n (%)	n (%)
African	n (%)	n (%)	n (%)	n (%)
American/Black	n (%)	n (%)	n (%)	n (%)
Other	n (%)	n (%)	n (%)	n (%)
p-value	p	p	p	p
Body mass index				
< 25 kg/m 	n (%)	n (%)	n (%)	n (%)
≥ 25 kg/m 	n (%)	n (%)	n (%)	n (%)
p-value	p	p	p	p
Baseline facial IGA				
Moderate	n (%)	n (%)	n (%)	n (%)
Severe	n (%)	n (%)	n (%)	n (%)
p-value	p	p	p	p
Female who used oral contraceptive*				
Used	n (%)	n (%)	n (%)	n (%)
Did not use	n (%)	n (%)	n (%)	n (%)
p-value	p	p	p	p

Note: Data from Clinician DCF; X patients had missing data; The denominator for the percentages is the number of patients with available data (N=X)

\* The denominator for the percentages is the number of 'female' patients with available data (N=X)

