**Figure 8.6 Clinician Acne Evaluation (IGA Success) (with LOCF imputation)**

*Figure 8.6 corresponds to Table 7.2.4.4. Clinician Acne Evaluation (IGA) (with LOCF imputation) with % of clear/almost clear category*

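### LOCF counts every missed Week-4 IGA as a non-response, and the Week-4/8 subgroup tables and related figures have no observed-value version

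*SAP*

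**What the plan says.** **The rule.** SAP 6.9 covers three measures: IGA, ASIS item 9 and ASIS item 10. After setting LOCF for Week 12 it adds that "LOCF will also be used to impute responses for Weeks 4 & 8 for the Subjects with missing data at those encounters", with an undefined as-appropriate qualifier. SAP 6.6.4 repeats the rule for the patient items without the qualifier: "LOCF data imputation method will be used to impute responses to ASIS items # 9 & 10 for respective encounters". Protocol 12.6.4 has the same rule for items 9 and 10. Protocol 12.7 only permits LOCF at Weeks 4 and 8; the SAP makes it definite.

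**What can be carried forward.** SAP 4 lists four encounters: baseline and Weeks 4, 8 and 12. SAP 5.3.1 places the baseline IGA before treatment starts. SAP 3.1 requires of each patient: "Has facial non-nodular AV with IGA score of moderate (3) or severe (4".

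**Who is analysed.** Under SAP 6.2 and 7 the FAS is in essence the Week-12 survey completers. For IGA and physician satisfaction, SAP 7.2 adds that "only FAS dataset with corresponding week 12 clinician data is used". SAP 6.5, 6.9 and 6.11 nevertheless still provide for missing Week-12 values.

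**Missed visits.** SAP 6.10 states that "patients are expected to miss clinic visits or reschedule planned visits as life situations change" and does not treat this as a deviation. SAP 6.3.1 assumes that missing data are uninformative.

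**Outputs that cover Weeks 4 and 8.**
- Overall cohort without imputation: Tables 7.1.12, 7.1.13, 7.2.4.1, 7.2.4.2.
- Overall cohort with LOCF: Tables 7.1.14, 7.1.15, 7.2.4.4, 7.2.4.6.
- LOCF only: subgroup Tables 7.1.16.1, 7.1.16.2 and 7.2.4.5; Table 7.5.1 by visit type; Figures 8.3 and 8.4 (drawn from Table 7.1.14) and Figure 8.6 (drawn from Table 7.2.4.4).

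**The concern.** A patient who misses Week 4 but returns at Week 12 has not dropped out. The gap is intermittent and a later value exists. LOCF ignores that value and inserts an older one, which at Week 4 can only be baseline. For IGA this turns a missed appointment into a recorded non-response.

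Two things are at stake. The described time course can look slower than it was. And the subgroup tables print p-values at Weeks 4 and 8: if one subgroup misses more visits than another, its percentage falls for that reason alone. No companion table would show the reader that this had happened.

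**Working it through.** The documents give no response rate, missed-visit rate or power figure, so there is no planned number to reproduce. All rates below are assumptions. Let m be the share missing a visit, p4 and p8 the clear/almost-clear rates at Weeks 4 and 8, and b the favourable share at baseline.

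**1. Week-4 IGA.** Suppose r of N patients are observed as clear/almost clear. The observed rate is r / [N(1 − m)]. Imputed patients carry a 3 or 4 and add nothing to r, so the LOCF rate is r / N, which equals the observed rate × (1 − m). This is an identity under any missingness mechanism. Full data could only add successes among those who missed, so the LOCF rate cannot exceed the full-data rate.
- 25% observed, m = 10%: 0.25 × 0.90 = 22.5%.
- 25% observed, m = 20%: 0.25 × 0.80 = 20.0%.

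**2. Week-8 IGA.** With independent misses, the LOCF rate is (1 − m)p8 + m(1 − m)p4. At p4 = 20%, p8 = 45% and m = 10% this is 0.405 + 0.018 = 42.3%, a loss of 2.7 points. Over p4 = 10–30%, p8 = 30–45% and m = 5–20% the loss ran from 0.1 to 7.4 points. A Week-4 success carried to Week 8 counts as a success, so the direction depends on average improvement between visits.

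**3. ASIS items 9 and 10.** Eligibility sets no floor on these, so b can exceed zero. The Week-4 LOCF rate is (1 − m)p4 + m·b. At p4 = 30% and m = 10%, b from 0 to 10% gives 27.0% to 28.0%. The direction again requires improvement, here p4 > b.

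**4. Subgroup p-values at Week 4, IGA.** Take two subgroups with the same 25% response, 125 patients each (assumed), but unequal missingness. The printed rates are 0.25(1 − m1) and 0.25(1 − m2), with difference d. With z = d / √{[P1(1 − P1) + P2(1 − P2)] / 125}, the two-sided rejection rate at 5% is about Φ(z − 1.96) + Φ(−z − 1.96).

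| Missing | Printed rates | z | Rejection |
|---|---|---|---|
| 5% v 10% | 23.75% v 22.50% | 0.23 | 5.6% |
| 5% v 15% | 23.75% v 21.25% | 0.47 | 7.6% |
| 5% v 25% | 23.75% v 18.75% | 0.97 | 16.2% |

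Exact binomial enumeration of the same comparisons gives 5.5%, 7.4% and 15.9%, against 4.9% with nobody missing.

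**5. Dependence on why visits are missed.** A simulation of Week-4 IGA gave:

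| Who misses | Full data | Observed only | LOCF |
|---|---|---|---|
| Unrelated to response | 20.4% | 20.4% | 18.4% |
| Mostly poor responders | 20.4% | 22.7% | 19.6% |
| Mostly good responders | 20.3% | 16.8% | 14.6% |

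LOCF was low in all three. Observed values were right only when misses were unrelated to response, which is what the SAP assumes.

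**The case against.** Several counter-arguments have force.

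- **Only supportive timepoints are involved.** The primary and secondary endpoints are at Week 12, and SAP 6.3.1 treats p-values as exploratory. Table 7.5.1 has no p-value. This stands. A reader might infer that the main endpoints are biased; where Week 12 is observed, the Week-4/8 rule does not touch them.
- **Observed-value tables are planned.** This is true for the overall cohort, where the LOCF effect can be read off directly. It does not extend to the LOCF-only outputs, and SAP 6.11 limits its with-and-without comparison to Week 12.
- **The as-appropriate wording leaves room.** It is undefined, and the sentence still says LOCF will be used. SAP 6.6.4 has no such qualifier, though it covers only items 9 and 10.
- **The bias does not flatter the drug.** For Week-4 IGA this is correct, since LOCF lowers apparent response. The subgroup comparison can still be distorted.
- **Observed values can also be biased.** This stands too. If poor responders miss more visits, LOCF can land nearer the full-data rate, as the second simulation row shows. The case for observed values rests on the SAP's own uninformative-missingness assumption.

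A reader might also infer that LOCF always carries a pre-treatment value. That is exact for IGA, but protocol section 7 lets baseline data collection run to 4 days after the first dose, so a baseline survey may fall on treatment.

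**Conclusion.** The point holds in a limited form. For Week-4 IGA the loss is certain: relative to the observed rate, it equals the share of visits missed. For Week 8 and for ASIS items 9 and 10 it occurs only if patients improve on average between the carried and the missed visit. The documents do not support the broader reading that all on-treatment response is understated.

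The practical weakness is that the Week-4/8 subgroup tables, Table 7.5.1 and Figures 8.3, 8.4 and 8.6 have no observed-value counterpart. The inflation of exploratory p-values is small under modest imbalance: about 6% at 5% v 10% missing and 7–8% at 5% v 15%. The figure of 16% needs a 5% v 25% split, for which the documents give no evidence, and should not be read as the expected error rate.

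That the gaps are intermittent follows from the FAS definition and SAP 7.2. SAP 6.5, 6.9 and 6.11 still allow for missing Week-12 values, and the two positions need reconciling.

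**What to change.** 1. In SAP 6.6.4 and 6.9, make observed values the basis for Weeks 4 and 8, with change from baseline computed in patients who have both values. Apply this to Tables 7.1.16.1, 7.1.16.2, 7.2.4.5 and 7.5.1.
2. At Weeks 4 and 8, re-source Figures 8.3 and 8.4 to Table 7.1.12 and Figure 8.6 to Table 7.2.4.1, so that figures and tables agree.
3. In Tables 7.1.14, 7.1.15, 7.2.4.4 and 7.2.4.6, either drop the Week-4/8 columns or label them as sensitivity results.
4. Use observed values at Weeks 4 and 8 in Tables 7.3.1–7.3.4. SAP 6.3.1 specifies LOCF for the interim patient–clinician severity comparison, so align it.
5. State that these results rely on uninformative missingness. The repeated-measures analysis allowed in protocol 12.3.3 can be added as support.
6. Record the change as a departure from protocol 12.6.4, and reconcile the FAS definition and SAP 7.2 with the Week-12 provisions in SAP 6.5, 6.9 and 6.11.

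Two separate corrections belong in the same edit. Tables 7.1.14 and 7.1.15 impute the caregiver severity item Q1, although SAP 6.9 limits imputation to the three named measures and SAP 6.6.5 says of the caregiver comparisons "No missing data imputation will be undertaken for these items"; remove that item. SAP 7.5 also describes these two tables as not imputed, contrary to their titles.

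The cost is SAP wording, a changed input dataset for the listed outputs, a documented protocol departure, and Week-4/8 denominators reduced by however many visits were missed.

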## 6.10 Significant Protocol Deviations

A protocol deviation is defined as any intentional or unintentional failure to follow the requirements and procedures described in the study protocol. Deviations may have occurred at the subject level or at the site level, and could have been recorded by the site, or uncovered data review. Considering the real-world study design of PROSES, reflecting the routine clinical practices in the U.S and associated patient encounters and routine/standard of care data documentation, patients are expected to miss clinic visits or reschedule planned visits as life situations change. These will not be considered as protocol deviations.

Significant protocol deviations will be flagged, and these are defined as study-related issues that were likely to result in: significant impairment of the rights, welfare or safety of subjects; misconduct and/or fraud; and significant impairment of the integrity/validity of study results. Significant protocol deviations also include issues that were likely to impair monitoring and oversight of the study.

## 6.11 Sensitivity Analyses

Sensitivity analyses will explore the impact of critical missing data or variation in study procedures on the robustness of the results. Specifically:

- Primary and secondary endpoints at Week-12 will be analyzed as is (with missing data, if any) and by using missing data imputation methods (using LOCF; in case of missing data observed), and results portrayed separately for comparison.
- If some Subject visits are conducted via remote visits instead of in-person visits, the nature of visit (remote vs. in-person) may be used to stratify the analysis of secondary endpoint

(involving IGA) and results portrayed separately for comparison with the overall (aggregate) results.

## 7 DATA TABLES

All patients who received at least one dose of sarecycline during the study observation period and had at least some data pertaining to ASIS and EPQ items (related to primary research objective) at Week 12 will be included in **Full Analysis Set (FAS)** to facilitate the planned descriptive analysis. Correspondingly, patients who completed the study survey at Week 12 will be included in FAS, since patients answering Week 12 survey will have completed all relevant PRO related questions.

Safety data analyses will be conducted among the Safety Population, that correspond to the entire study cohort that took at least one does of sarecycline. Correspondingly, all patients completing the baseline survey and took at least one dose of sarecycline, amounting to N=300 will be included in this analysis.

## 7.1 Patient Demographics, Perceptions & PROs (FAS Population)

Patient data analysis including demographics, perceptions, and PRO data is analyzed using the FAS dataset. All results depicted in this section pertain to FAS Population.

**Table 7.1.1. FAS Population**

S1: Population	N=x
Adult Patient	n (%)
Pediatric Patient & Caregiver	n (%)
Total Population	n (%)

Note: Data from Patient DCF

**Table 7.1.2. Adult Patient & Caregiver Demographic characteristics**

Adult Demographic Data	Caregiver N=x	Adult Patient N=x	Total N=x
S2: Age	mean (SD) Median Min, Max	mean (SD) Median Min, Max	mean (SD) Median Min, Max
S8: Gender			
Male	n (%)	n (%)	n (%)
Female	n (%)	n (%)	n (%)
S9: Marital Status			
Not Married	n (%)	n (%)	n (%)
Not Marries, living with Partner	n (%)	n (%)	n (%)
Married or Civil Union	n (%)	n (%)	n (%)
Divorced or Separated	n (%)	n (%)	n (%)
Widow/Widower	n (%)	n (%)	n (%)
Prefer not to answer	n (%)	n (%)	n (%)
S10: Highest level of Education			
Less than high school	n (%)	n (%)	n (%)
diploma/degree		n (%)	n (%)
High school degree or equivalent (e.g., GED)	n (%)	n (%)	n (%)
Some college but not degree	n (%)		
Associated degree	n (%)	n (%)	n (%)
Bachelor's degree	n (%)	n (%)	n (%)
Graduate degree	n (%)	n (%)	n (%)
Prefer not to answer	n (%)	n (%)	n (%)
S11: Employment status			
Employed/Working full-time (paid)	n (%)	n (%)	n (%)
Employed/Working part-time (paid)	n (%)	n (%)	n (%)
Homemaker	n (%)	n (%)	n (%)
Student	n (%)	n (%)	n (%)
Retired	n (%)	n (%)	n (%)
Unemployed	n (%)	n (%)	n (%)
S12: Annual household income			
\$20,000 or less	n (%)	n (%)	n (%)
\$20,001-\$50,000	n (%)	n (%)	n (%)
\$50,001-100,000	n (%)	n (%)	n (%)
\$100,001 or more	n (%)	n (%)	n (%)
Prefer not to answer	n (%)	n (%)	n (%)
S13: Regions/States			
Northeast	n (%)	n (%)	n (%)
Midwest	n (%)	n (%)	n (%)

West	n (%)	n (%)	n (%)
South	n (%)	n (%)	n (%)
S14: Number of children (aged 0 to 17)			
No children	n (%)	n (%)	n (%)
1	n (%)	n (%)	n (%)
2	n (%)	n (%)	n (%)
3	n (%)	n (%)	n (%)
4	n (%)	n (%)	n (%)
More than 4	n (%)	n (%)	n (%)
S16: Primary Health Insurance			
Private health insurance	n (%)	n (%)	n (%)
Medicaid	n (%)	n (%)	n (%)
Medicare	n (%)	n (%)	n (%)
Uninsured	n (%)	n (%)	n (%)
S17: Race/Ethnicity*			
S17r1: White	n (%)	n (%)	n (%)
S17r2: Black or African American	n (%)	n (%)	n (%)
S17r3: American Indian or Alaska Native	n (%)	n (%)	n (%)
S17r4: Asian	n (%)	n (%)	n (%)
S17r5: Native Hawaiian or other Pacific Islander	n (%)	n (%)	n (%)
S17r6: Other	n (%)	n (%)	n (%)
S17r7: Prefer not to answer	n (%)	n (%)	n (%)
S18: Hispanic, Latino, or of Spanish Origin			
Yes	n (%)	n (%)	n (%)
No	n (%)	n (%)	n (%)

\*Not mutually exclusive. Note: Data from Patient DCF.

**Table 7.1.3. Pediatric Patient Demographic Characteristics**

Pediatric Demographic Data	N=x
S3: Age	mean, SD, Median Min, Max
S21: Gender	
Male	n (%)
Female	n (%)
S22: Race/Ethnicity*	
S22r1: White	n (%)
S22r2: Black or African American	n (%)
S22r3: American Indian or Alaska Native	n (%)
S22r4: Asian	n (%)
S22r5: Native Hawaiian or other Pacific Islander	n (%)
S22r6: Other	n (%)
S22r7: Prefer not to answer	n (%)
S23: Hispanic, Latino, or of Spanish Origin	
Yes	n (%)
No	n (%)
S24: Child's Academic Accomplishments	
Current/Last grade completed:	
Pre-K - 5 th grade	n (%)
6 th grade – 8 th grade	n (%)
9 th grade – 12 th grade	n (%)
High School Diploma/Degree	n (%)
Vocational School	n (%)
Not currently enrolled in school	n (%)
S24oe: Other	n (%)

\*Not mutually exclusive

Note: Data from Patient DCF

**Table 7.1.4. Select Patient Demographics from Clinician Data**

Demographic Data	N=x
M1B: Gender	
Male	n (%)
Female	n (%)
M2: Primary Health Insurance	
Private health insurance	n (%)
Medicaid	n (%)
Medicare	n (%)
Uninsured	n (%)

Note: Data from Clinician DCF

**Table 7.1.5 Antibiotic Attitudes**

Antibiotic Attitudes	Adult Patient	Caregiver
	N=x	N=x
Q5: How concerned are you about [your child] using antibiotics for acne?	Mean (SD), Median, Min,Max	Mean (SD), Median, Min,Max
Not at all (0)	n (%)	n (%)
Slightly (1)	n (%)	n (%)
Somewhat (2)	n (%)	n (%)
Moderately (3)	n (%)	n (%)
Extremely (4)	n (%)	n (%)
S20c: How concerned are you about antibiotic resistance?	Mean (SD), Median, Min,Max	Mean (SD), Median, Min,Max
Not at all (0)	n (%)	n (%)
Slightly (1)	n (%)	n (%)
Somewhat (2)	n (%)	n (%)
Moderately (3)	n (%)	n (%)
Extremely (4)	n (%)	n (%)

Note: Data from Patient DCF; X patients had missing data; The denominator for the percentage is the number of patients with available data (N=XX)

**Table 7.1.6.1 Expert Panel Questions (EPQs)**

	Baseline (N=x)	Week 12 (N=x)
Emotional Functioning EPQ1 (AH1): Over the past 7 days, how often has your acne made you feel angry (mad/sad)?	Mean (SD), Median, Min,Max	Mean (SD), Median, Min,Max
Never (0)	n (%)	n (%)
Rarely (1)	n (%)	n (%)
Some of the time (2)	n (%)	n (%)
Most of the time (3)	n (%)	n (%)
All of the time (4)	n (%)	n (%)
Emotional Functioning EPQ2 (AH2): How worried are you about how long your acne will last and how bad it will get?	Mean (SD), Median, Min,Max	Mean (SD), Median, Min,Max
Not at all (0)	n (%)	n (%)
Slightly (1)	n (%)	n (%)
Somewhat (2)	n (%)	n (%)
Moderately (3)	n (%)	n (%)
Extremely (4)	n (%)	n (%)
Emotional Functioning EPQ3 (AH3): How often do you think about your acne?	Mean (SD), Median, Min,Max	Mean (SD), Median, Min,Max
Never (0)	n (%)	n (%)
Rarely (1)	n (%)	n (%)
Some of the time (2)	n (%)	n (%)
Most of the time (3)	n (%)	n (%)
All of the time (4)	n (%)	n (%)
Emotional Functioning EPQ4 (AH4): Over the past 7 days, how worried have you been about your acne?	Mean (SD), Median, Min,Max	Mean (SD), Median, Min,Max
Not at all (0)	n (%)	n (%)
Slightly (1)	n (%)	n (%)
Somewhat (2)	n (%)	n (%)
Moderately (3)	n (%)	n (%)

Extremely (4)	n (%)	n (%)
Social Functioning		
EPQ5 (AH5): How often do you change, edit, or filter your social media photo or selfie because of your acne?	Mean (SD), Median, Min,Max	Mean (SD), Median, Min,Max
Never (0)	n (%)	n (%)
Rarely (1)	n (%)	n (%)
Some of the time (2)	n (%)	n (%)
Most of the time (3)	n (%)	n (%)
All of the time (4)	n (%)	n (%)
Social Functioning		
EPQ6 (AH6): How often does acne impact your “in real-life” plans (IRL) (like dating or social engagements, playing sports, swimming or hanging out)?	Mean (SD), Median, Min,Max	Mean (SD), Median, Min,Max
Never (0)	n (%)	n (%)
Rarely (1)	n (%)	n (%)
Some of the time (2)	n (%)	n (%)
Most of the time (3)	n (%)	n (%)
All of the time (4)	n (%)	n (%)
Social Functioning		
EPQ7 (AH7): How often are you doing something to hide your acne (like mess with, squeeze/pop, or use makeup, concealer, hairstyle, clothes to cover up)?	Mean (SD), Median, Min,Max	Mean (SD), Median, Min,Max
Never (0)	n (%)	n (%)
Rarely (1)	n (%)	n (%)
Some of the time (2)	n (%)	n (%)
Most of the time (3)	n (%)	n (%)
All of the time (4)	n (%)	n (%)
Activities of Daily Living		
EPQ8 (AH8): How often do you feel picked on or judged because of your acne?	Mean (SD), Median, Min,Max	Mean (SD), Median, Min,Max
Never (0)	n (%)	n (%)

Rarely (1)	n (%)	n (%)
Some of the time (2)	n (%)	n (%)
Most of the time (3)	n (%)	n (%)
All of the time (4)	n (%)	n (%)
Activities of Daily Living		
EPQ9 (AH9): How concerned are you that your acne will affect your ability to reach your future goals (in school or work) and be the best you can be?	Mean (SD), Median, Min,Max	Mean (SD), Median, Min,Max
Not at all (0)	n (%)	n (%)
Slightly (1)	n (%)	n (%)
Somewhat (2)	n (%)	n (%)
Moderately (3)	n (%)	n (%)
Extremely (4)	n (%)	n (%)
Activities of Daily Living		
EPQ10 (AH10): Do you feel that your parents understand your acne-related concerns?	Mean (SD), Median, Min,Max	Mean (SD), Median, Min,Max
Not at all (0)	n (%)	n (%)
A little (1)	n (%)	n (%)
Somewhat (2)	n (%)	n (%)
Quite a bit (3)	n (%)	n (%)
Very Much (4)	n (%)	n (%)
Activities of Daily Living		
EPQ11 (AH11): Over the past 7 days, how often has worrying about or discomfort (itching/hurting) from acne affected your sleep?	Mean (SD), Median, Min,Max	Mean (SD), Median, Min,Max
Never (0)	n (%)	n (%)
Rarely (1)	n (%)	n (%)
Some of the time (2)	n (%)	n (%)
Most of the time (3)	n (%)	n (%)
All of the time (4)	n (%)	n (%)

Note: Data from Patient DCF; X patients had missing data; The denominator for the percentage is the number of patients with available data (N=XX)

Note: For All EPQ items, the responses are re-coded to 0-4, from 1-5 in the study database.

